Relative dose intensity will be calculated using the methods described by Longo et al [24]. The primary endpoint, RDI will be analyzed both as a continuous scale using the t test, and as a dichotomized outcome using 85% or 95% cut-off for Mantel-Haensel chi-square test controlling for stratification factors. In addition, group differences in chemotherapy completion rates will be analyzed with binary logistic regression analysis; whether or not having dose reduction during the period of chemotherapy treatment (the period between T0 and T1) will be the dichotomized dependent variable. The outcome of endocrine therapy adherence will be assessed at the 2 and 5-year follow ups (as most, if not all, participants prescribed endocrine therapy will have been taking it for at least 1 year at the 2-year visit, allowing us to assess adherence to endocrine therapy). The primary endocrine therapy outcome will be adherence to endocrine therapy assessed via the electronic medical records. Note: the assessment for the primary outcome of endocrine therapy adherence was changed from the initial assessment (urinary metabolites) as the COVID pandemic limited our ability to collect urine samples.

Secondary assessments of endocrine therapy will be:

a) Urinary AI level. An undetectable level will classify the participant as nonadherent to AIs.

b) Responses to the following questions:

(1) “In the past month, how often did you take your medications as the doctor prescribed?” Possible responses are all of the time (100%), nearly all of the time (90%), most of the time (75%), about half the time (50%), or less than half the time (<50%). Nonadherence is defined as 75% of the time or less.

(2) “In the past month, how often did you forget to take 1 or more of your prescribed medications?”

Possible responses were never, once in the past month, 2 to 3 times in the past month, once per week, several times per week, and nearly every day. Nonadherence is defined as forgetting to take prescribed medications once per week or more.

(3) “In the past month, how often did you decide to skip 1 or more of your prescribed medications?”

Possible responses were the same as for question 2. Nonadherence is defined as deciding to skip medications once per week or more. The first will be the primary measure of non-adherence. (73,74).

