Participants who report that they have discontinued taking tamoxifen or AI will also be classified as nonadherent to endocrine therapy. For patients who may be lost to follow-up, we will obtain prescription refill data as an endpoint of adherence to endocrine therapy. For the endocrine

therapy aim, we will compare the crude adherence rates using simple logistic regression. Multivariate logistic regression will serve as supportive analyses including covariate adjustments – which are similar to the primary analysis above.

The secondary aims will be performed using Mixed Model Repeated Measures analysis incorporating Analysis of Covariance, where each woman's changes in outcome (follow-up measure – baseline) will be modeled as a function of treatment and time with a covariate included for the baseline value. Prior to fitting models, we will perform exploratory data analyses focusing on the distributions of biological markers by time and intervention group, assessing the appropriateness of log-transformation.

All hypotheses will be tested according to the intention-to-treat philosophy in which all randomized participants will be grouped according to their intervention assignment at randomization, regardless of compliance or adherence to the study. Statistical significance will be defined as $p < 0.05$, 2-sided. Since we have multiple outcomes, we will consider using a Bonferroni correction.

Age, menopausal status, race/ethnicity, BMI at diagnosis, disease stage, type of surgery, type of chemotherapy, radiation therapy, hormone receptor status, endocrine therapy, reconstructive surgery, type 2 diabetes, and smoking status will be examined as covariates. We will explore effect modification by menopausal status at diagnosis, hormone receptor status, and endocrine therapy.

We will further explore intervention effects on study endpoints by stratifying by adherence to diet and physical activity guidelines with a four-level category (e.g., met diet recommendations, met physical activity, met both diet and physical activity recommendations, or met neither recommendation). This analysis will allow us to better understand the role of diet vs. exercise on study endpoints.

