Although we do not anticipate an appreciable number of subjects lost-to-follow-up because of our plan of following patients during their medical oncology visits, the impact of missing data will be evaluated in the analysis. Bivariate logistic regression will be used to identify baseline variables associated with missingness. The primary analysis assumes missing data are missing at random (MAR). Under the MAR missing data mechanism, the probability of loss-to-follow-up depends only on the observed data. Non-random or informative loss-to-follow-up occurs when the missing data are dependent on the unobserved missing outcome values, latent and/or instrumental variables. Sensitivity analyses using methods for NMAR data will be considered.

Power and Sample Size Considerations: The sample size estimate was performed using PASS 12 (©2013 NCSS, LLC, Kayesville, UT). The original calculation was based on chemotherapy completion rates reported in the COMPAS study (Ziller etc, BMC Cancer, 2013). By assuming similar completion rate in our control arm, we estimated a sample size of 250 subjects would be needed. Sample size reevaluation was conducted using the aggregated data of first 51 LEANer participants who completed chemotherapy. The pooled standard deviation of RDI is 0.10. We re-estimated that a sample size of 86 subjects per arm (172 total) will achieve 90% power to detect a 0.05 (or 5%) difference in RDI between two arms at significance level of 0.05. For endocrine therapy adherence, the COMPAS study reported 48% of patients in the control group were adhering to AI therapy at 12 months.¹⁸ We assume approximately 50% of patients randomized to usual care in our study will be adhering to endocrine therapy at one-year post-initiation of use. Group sample sizes of 76 patients per group (or $N = 152$) provides 90% power to detect an absolute difference of 25% in the intervention group (50% vs. 75%, adherence in control and intervention groups, respectively) at a two-sided 0.05 significance level. We anticipate ~70% of participants (i.e., 70% of 172 = 120) will be prescribed endocrine therapy; thus an $N = 120$ will also allow for sufficient statistical power.

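### MAR is assumed for the primary analysis, but the RDI t test and crude adherence comparison use no covariates and name no missing-data method; the t test also ignores the stratification factors

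*Combined protocol and SAP*

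**What the plan says.** All of the relevant analysis text is in Section I, item 12 (Statistical Considerations).

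- **Assumption.** "The primary analysis assumes missing data are missing at random (MAR"). The plan explains the term itself: "Under the MAR missing data mechanism, the probability of loss-to-follow-up depends only on the observed data".
- **RDI.** "RDI will be analyzed both as a continuous scale using the t test". A dichotomised version (85% or 95% cut-off) uses a Mantel-Haenszel "chi-square test controlling for stratification factors".
- **Endocrine adherence.** "we will compare the crude adherence rates using simple logistic regression". Adjustment is secondary: "Multivariate logistic regression will serve as supportive analyses including covariate adjustments". The same sentence likens those adjustments to the primary analysis above it, although the t test above it has none.
- **Missingness.** "Bivariate logistic regression will be used to identify baseline variables associated with missingness". No use for those variables is then given. Analyses for data not missing at random (NMAR) are only to be considered.
- **Mixed model for repeated measures.** This is planned for the secondary aims only.
- **Randomisation** (Section I, item 3(d)). It is stratified by number of chemotherapy cycles, hormone receptor status and HER2 status, chosen because they may be related to some endpoints.

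**The concern.** MAR allows missingness to depend on observed data. An analysis gains protection from that assumption only if it uses those data, through covariates, imputation, weighting or a likelihood that includes them. For the two primary comparisons the plan describes none of these, so the stated assumption and the stated methods are not connected.

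Differential loss is conceivable. Intervention women have 16 counselling sessions over a year and usual-care women do not (item 3(d)). The target outside Yale is 172 − 133 = 39 women (Section III, item 1). For self-referred Columbia patients, records depend on a signed release and are requested at the end of chemotherapy (item 3(b)), before the 2- and 5-year adherence assessments. Site is therefore an observed, plausible predictor of missing adherence data, but it is in neither the primary models nor the list of covariates to be examined.

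A second, separate matter is precision. The randomisation controls for three factors that the t test leaves in the error term.

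**Working it through.** **1. The plan's own figure.** Inputs (item 12, Power and Sample Size Considerations): difference 0.05, SD 0.10, two-sided 0.05, power 90%.

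n per arm = 2(1.960 + 1.282)² × 0.10² / 0.05² = 84.1, so 85. The exact t-test calculation gives 85.03, so 86, with power 0.903 at 86. The stated 86 per arm reproduces.

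**2. When the unadjusted comparison is biased.** Suppose women without an outcome are left out. With stratum shares π(x), missing probabilities m(a,x) and means μ(a,x), the expected mean in arm a is

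Σ π(x)[1 − m(a,x)] μ(a,x) / Σ π(x)[1 − m(a,x)].

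The difference between arms is unbiased if m depends on arm only, or if m depends on x identically in both arms and the effect is constant. It is biased if x is prognostic and its link to missingness differs by arm.

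**3. RDI illustration.** The documents give no missing rate, so the rates and stratum means are assumed. Shares are 1/3 (≤4 cycles) and 2/3 (>4 cycles), in line with the regimen mix in the usual-care description. Usual-care means are 0.95 and 0.85, and the true difference is 0.05. Loss is 5% everywhere except usual-care women with >4 cycles.

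- Intervention mean: 0.95/3 + 2 × 0.85/3 + 0.05 = 0.9333.
- Usual care, 20% loss: (0.3167 × 0.95 + 0.5333 × 0.85)/0.8500 = 0.8873; difference 0.046.
- Usual care, 30% loss: (0.3167 × 0.95 + 0.4667 × 0.85)/0.7833 = 0.8904; difference 0.043.

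The bias is 0.004 to 0.007, or 0.24 to 0.43 standard errors, and here it is towards no effect.

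**4. General illustration with no true effect.** Assumed: a binary factor with 50% prevalence shifts RDI by 0.10, total SD is 0.10, and there are 86 women per arm (6,000 simulated trials, Monte Carlo error about 0.003). For adherence, rates are assumed to be 35% and 65% by the factor.

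| Missingness | Expected RDI bias | Type I error, t test | Type I error, factor in model | Crude adherence OR (true 1.00) |
|---|---|---|---|---|
| Depends on arm only | 0 | 0.050 | 0.044 | not run |
| 10% per arm, same dependence in both | 0 | 0.055 | 0.052 | 1.00 |
| 10% per arm, dependence in one arm only | 0.006 | 0.062 | 0.049 | 1.07 |
| 10% per arm, opposite dependence | 0.011 | 0.106 | 0.051 | 1.14 |
| 20% per arm, opposite dependence | 0.025 | 0.313 | 0.049 | 1.35 |

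At 5% missing per arm the RDI bias is 0 to 0.005. Putting the factor in the RDI model removes the bias in every row.

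**5. Precision, with nothing missing.** Assume a 0.10 RDI gap between cycle strata with shares 1/3 and 2/3, within the stated total SD.

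- Residual variance: 0.0100 − (1/3)(2/3)(0.10)² = 0.00778, so residual SD 0.0882.
- Standard error: 0.10 × √(2/86) = 0.01525 as the t test computes it, against 0.0882 × √(2/86) = 0.01345 adjusted. The ratio is 1.13.
- Adjusted power at 86 per arm: standardised difference 0.05/0.0882 = 0.567, power 0.959, against the nominal 0.903.

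If stratification balances the arms exactly, the t test's estimate also varies with standard error 0.01345, but it is judged against 0.01525. Its type I error is then about 2[1 − Φ(1.974 × 0.01525/0.01345)] = 0.025. Its power is about Φ[(0.05 − 1.974 × 0.01525)/0.01345] = 0.93. The real gain is then from about 0.93 to 0.96. With an assumed gap of 0.05, residual SD is 0.0972 and the gain is from 0.910 to 0.918.

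**The case against.** A reader might infer that the two primary tests are simply invalid under MAR, that they drop every woman without an outcome, and that endocrine adherence is badly exposed. The documents do not support this.

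- **Invalid under MAR.** This is too strong. Bias needs a prognostic factor that acts on missingness differently by arm; the first two table rows show none.
- **Complete cases.** This is inferred. The plan does not say how a missing primary outcome is handled, and for adherence it provides for prescription refill data on women lost to follow-up.
- **Exposure.** Both primary outcomes are taken from medical records, so they do not require a study visit. Yale supplies 133 of the 172 women, DFCI staff record chemotherapy data after each session, and the signed release is described only for Columbia patients. The plan expects no appreciable loss. Nothing in the documents points to the 20% opposite-pattern case.
- **Partial handling.** The dichotomised RDI test is stratified and an adjusted logistic model is supportive for adherence. The reference to adjustments like those of the primary analysis may mean that adjustment was also intended for RDI.
- **Remedy.** Adding variables found to predict missingness to the primary model would make that model depend on the data. At 5% missing there would be about 0.05 × 172 ≈ 9 missing outcomes, too few to choose predictors reliably. Adjusted logistic regression also replaces the marginal odds ratio with a conditional one.

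All of this stands, and it limits the size of the problem. It does not supply the method that the MAR statement needs, and it does not answer the precision point.

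**Conclusion.** The concern holds in a limited form. The plan assumes MAR but names no method that uses the observed data for the t test or the crude logistic regression, so neither is guaranteed valid under that assumption. The likely bias is small: 0.004 to 0.007 against a target difference of 0.05 in the RDI illustration, and at most about 0.005 with 5% missing in the general one. It becomes material only with substantial loss that follows different patterns in the two arms. All missing rates and covariate strengths here are assumptions.

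The precision point does not depend on missing data. If the stratification factors predict RDI, the t test's standard error is too large and the test is conservative. The gain from adjustment ranges from negligible to several points of power, depending on how strongly they predict it.

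**What to change.** 1. Make the primary analysis of continuous RDI a linear regression on arm and the three pre-specified stratification factors. Keep the t test as supportive.
2. Adjust the primary adherence comparison for the stratification factors that apply to women on endocrine therapy (cycles and HER2 status, since receptor status hardly varies among them). Report a standardised risk difference so that the estimand stays marginal. Keep the crude logistic regression as supportive.
3. State how a missing primary outcome is handled, including when refill data replace the record-based adherence outcome.
4. Use the identified predictors of missingness, with site added, in a multiple-imputation sensitivity analysis. Do not enter them as data-selected terms in the primary model.
5. Correct the sentence implying that the primary analysis already has covariate adjustments.

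The cost is SAP wording and a little more programming. No additional data or participants are needed.

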For insulin, our previous studies showed a 25-30% effect size (3.0 μ U/mL) and standard deviation of 8.0 μ U/mL, which yields a per group sample size of 112 or total N = 224.24 For weight changes, our LEAN study showed a 7% effect size (5.6 kg) and a SD of 4.2 kg in the intervention group compared to 2% (1.7 kg) and SD of 3.7 kg in usual care (P=0.0004). (24) We will have sufficient statistical power to detect smaller effect size since we will have a larger sample size in the current application.

We will not allow participants who are assigned into usual care cross over to intervention group. However, if 10% of 86 participants who are randomized into intervention arm drop out to usual care, we will have 81% power to detect difference of 18% chemotherapy dose adjustment in intervention vs 34% in controls.

SECTION II: RESEARCH INVOLVING DRUGS, BIOLOGICS, RADIOTRACERS, PLACEBOS AND DEVICES

If this section (or one of its parts, A or B) is not applicable, state N/A and delete the rest of the section.

A. RADIOTRACERS – N/A

B. DRUGS/BIOLOGICS – N/A

B. DEVICES – N/A

SECTION III: RECRUITMENT/CONSENT AND ASSENT PROCEDURES

1. Targeted Enrollment: Give the number of subjects:

- a. Targeted for enrollment at Yale for this protocol: 133
- b. If this is a multi-site study, give the total number of subjects targeted across all sites: 172

2. Indicate recruitment methods below. Attach copies of any recruitment materials that will be used.

- | | | |
|--|--|-------------------------------------|
|  Flyers |  Internet/Web Postings |  Radio |
|  Posters |  Mass E-mail Solicitation |  Telephone |
|  Letter |  Departmental/Center Website |  Television |
|  Medical Record Review* |  Departmental/Center Research Boards |  Newspaper |
|  Departmental/Center Newsletters |  Web-Based Clinical Trial Registries | |
|  YCCI Recruitment database |  Clinicaltrials.gov Registry (do not send materials to HIC) | |

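### The 90% RDI power behind N = 172 is correct as stated but makes no allowance for the plan's own 10% drop-out scenario, under which it lies between about 83% and 90%, depending on what the 0.05 means and when women leave

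*Combined protocol and SAP*

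**What the plan says.** All of the sizing text is in Section I, item 12 (Statistical Considerations) of the combined protocol and SAP.

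- Sizing, under Power and Sample Size Considerations: "The pooled standard deviation of RDI is 0.10", taken from the first 51 participants to complete chemotherapy. The sizing sentence follows from this value: "We re-estimated that a sample size of 86 subjects per arm (172 total) will achieve 90% power to detect a 0.05 (or 5%) difference in" mean relative dose intensity, where the difference is the one between the two arms and alpha is 0.05.
- Test, under Statistical Analyses: "RDI will be analyzed both as a continuous scale using the t test", and "Statistical significance will be defined as $p < 0.05$, 2-sided".
- Analysis set, same place: "all randomized participants will be grouped according to their intervention assignment at randomization, regardless of compliance or adherence to the study". This covers all hypotheses.
- Drop-out, in the last paragraph on power: "if 10% of 86 participants who are randomized into intervention arm drop out to usual care, we will have 81% power". That power is for dose adjustment in 18% of the intervention arm against 34% of controls. Movement from usual care to intervention is not allowed.

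No drop-out or dilution figure is given for RDI. The section expects no appreciable loss to follow-up, because patients are followed at their oncology visits.

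**The concern.** The plan treats drop-out to usual care as something that affects power, but works it through only for a supporting endpoint. The RDI comparison, which set the sample size, is given with no such allowance.

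Women who leave the programme stay in the intervention arm for analysis. RDI comes from medical records, so they would normally still contribute a value. If their RDI is that of usual care, they pull the arm means together. A reader of a null RDI result would then take 90% as the chance that the planned effect would have been found, when the plan's own scenario may put that chance lower.

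**Working it through.** **Inputs.** n = 86 per arm, SD = 0.10, difference = 0.05, two-sided alpha 0.05, two-sample t test, 10% of the intervention arm dropping out to usual care, analysis as randomized. All are from item 12.

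**1. Reproduce the stated 90%.** The noncentrality is difference / (SD × √(2/n)) = 0.05 / (0.10 × √(2/86)) = 0.05 / 0.01525 = 3.279. With 170 degrees of freedom the critical value is 1.974, and the noncentral t distribution gives power of 90.3%. At 85 per arm the power is 89.99%, so 86 is the bare requirement, with nothing added for non-adherence.

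**2. Apply the plan's 10% scenario to RDI.** Suppose the 0.05 is the effect in women who follow the programme, and women who leave keep a fraction k of it. The difference as analysed is 0.05 × (0.90 + 0.10k).

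| Case | Difference as analysed | Noncentrality | Power |
|---|---|---|---|
| All 10% leave early, k = 0 (full dilution) | 0.0450 | 2.951 | 83.5% |
| Half the effect kept, k = 0.5 (or half of the leavers go only after chemotherapy) | 0.0475 | 3.115 | 87.2% |
| All leave after chemotherapy, k = 1 | 0.0500 | 3.279 | 90.3% |

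Counting whole women, 9 of 86, full dilution gives 0.05 × 77/86 = 0.0448 and power of 83.1%. A simulation of the same case gave 82.6%.

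**3. The other meaning of 0.05.** If 0.05 is already the difference between the arms as randomized, power stays at 90.3%. Under full dilution the effect needed in women who follow the programme is then 0.05 / 0.90 = 0.0556, about 0.056.

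**4. Missing RDI instead of dilution.** If the 10% had no RDI value at all, power would be 88.6% (77 against 86) or 86.9% (77 in each arm).

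**5. Can the 81% for dose adjustment stand in for the allowance?** Normal approximation with pooled variance under the null: power = Φ[(|p1 − p2| − 1.96 × s0) / s1], where s0 is the pooled and s1 the unpooled standard error.

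- 18% against 34%, 86 per arm, no drop-out: (0.16 − 1.96 × 0.0669) / 0.0658 = 0.439, power 67%.
- 77 against 86: power 64%.
- Dilution as randomized, 0.90 × 18% + 0.10 × 34% = 19.6% against 34%, 86 per arm: (0.144 − 1.96 × 0.0675) / 0.0666 = 0.174, power 57%.
- 112 against 125, which is 10% lost from one arm of 125: power 80% (82% with unpooled variance).

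The 81% therefore does not reproduce at 86 per arm. It does fit the 125 per arm that still stands under Randomization in item 3, so it may be a carry-over from the total of 250. The documents do not say so.

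**The case against.** The strongest answer is that nothing stated is wrong. The 90% is right for its inputs, and the text speaks of a difference between two arms. Since the arms are analysed as randomized, the 0.05 can fairly be read as the intention-to-treat difference, already net of non-adherence. The documents nowhere call it the effect in women who follow the programme. This stands, and it is why the point is conditional.

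Timing also matters. RDI is settled during chemotherapy, which item 3 puts at about 3 to 5 months, while the programme runs for 12 months. Eleven of its 16 sessions fall in the first five months (3 + 2 × 4). The 10% scenario gives no timing. A woman who leaves after chemotherapy does not dilute RDI, and one who leaves midway may dilute it only in part. This stands too: 83% is the end of a range, not an estimate.

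The plan also has a reason for making no missing-data allowance. RDI comes from medical records, and stopping counselling does not remove it. That answers the question of missing outcomes but not dilution, because women who drop out to usual care are still counted in the intervention arm.

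A reader might infer that the sample size was miscalculated, that RDI power simply is 83%, or that the trial has to grow. The documents support none of these. The calculation reproduces, 83% needs both the narrower meaning of 0.05 and complete early loss of effect, and power stays above 80% even then. Restoring 90% in that worst case would take 105 per arm, but nothing in the plan shows that the worst case is the expected one.

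**Conclusion.** The point holds in conditional form, as a gap in reporting rather than an arithmetic error. The 90% is correct for a 0.05 difference between arms, but carries no allowance for the 10% drop-out that the plan itself raises.

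- If 0.05 is the effect in women who follow the programme, RDI power under that scenario is between about 83% and 90%, with about 87% if half the effect is kept. At the lower end, the chance of missing the planned effect rises from about 1 in 10 to about 1 in 6.
- If 0.05 is the intention-to-treat difference, 90% stands, and the programme must deliver about 0.056 in adherent women under full dilution.

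The assumptions are that women who leave have usual-care RDI for whatever part of the effect they lose, that their RDI is recorded, and that the SD of 0.10 holds. The documents do not settle which meaning of 0.05 was intended or when women would leave. The 81% for dose adjustment does not fill the gap.

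**What to change.** Keep N = 172. Under Power and Sample Size Considerations, directly after the 90% figure:

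1. State whether the 0.05 is the difference between arms as randomized or the effect in women who follow the programme.
2. Add the RDI power under the 10% scenario. For example: if 0.05 is the effect in women who follow the programme and 10% of the intervention arm drops out to usual care, RDI power as randomized is about 83% to 90%; the lower figure is the full-dilution case, in which all of them leave early and lose the whole effect (difference 0.045). If 0.05 is declared to be the difference as randomized, give instead the 0.056 needed in adherent women under full dilution.
3. Do not cite the 81% for dose adjustment as the existing allowance. Recalculate it at 86 per arm or remove it.

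The cost is two or three sentences and, on one reading, a less favourable power range beside the 90%. No patients, procedures or analyses change.

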- a. Does your YNHH privilege delineation currently include the **specific procedure** that you will perform? Yes No
- b. Will you be using any new equipment or equipment that you have not used in the past for this procedure? Yes No
- c. Will a novel approach using existing equipment be applied? Yes No

If you answered "no" to question 4a, or "yes" to question 4b or c, please contact the YNHH Department of Physician Services ([name]) for prior approval before commencing with your research protocol.

IMPORTANT REMINDER ABOUT RESEARCH AT YNHH

Please note that if this protocol includes Yale-New Haven Hospital patients, including patients at the HRU, the Principal Investigator and any co-investigators who are physicians or mid-level practitioners (includes PAs, APRNs, psychologists and speech pathologists) who may have direct patient contact with patients on YNHH premises must have medical staff appointment and appropriate clinical privileges at YNHH. If you are uncertain whether the study personnel meet the criteria, please telephone the Physician Services Department at [contact]. **By submitting this protocol as a PI, you attest that you and any co-investigator who may have patient contact has a medical staff appointment and appropriate clinical privileges at YNHH.**

SECTION I: RESEARCH PLAN

1. **Statement of Purpose:** State the scientific aim(s) of the study, or the hypotheses to be tested.

We propose to examine, in 172 women newly diagnosed with Stage I-III breast cancer who are not practicing the dietary and lifestyle guidelines, and who will receive neoadjuvant or adjuvant chemotherapy as part of their treatment, the effect of a 1-year dietary and physical activity guidelines intervention vs. usual care on the breast cancer outcomes described below. Women will be enrolled either before beginning chemotherapy or following the first chemotherapy infusion but prior to the second chemotherapy infusion (Time 0). Follow up visits will occur post chemotherapy (Time 1), at one-year post-diagnosis (Time 2), at two years post-diagnosis (Time 3) and at five years post-diagnosis.

Primary Endpoints: Adherence to Breast Cancer Treatments

Aim 1a: Chemotherapy completion rates (dose amount, number of dose reductions and dose delays)

Aim 1b: Adherence to endocrine therapy in women taking tamoxifen or Aromatase Inhibitors (AIs) at 12- and 24-months after enrollment

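### The endocrine-adherence endpoint is sized at 152 women for 90% power, but only about 120 are expected; the plan gives no power for 120, and by its own calculation it is about 82%

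*Combined protocol and SAP*

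**What the plan says.** Section I, item 1 (Statement of Purpose) lists this outcome under Primary Endpoints: "Aim 1b: Adherence to endocrine therapy in women taking tamoxifen or Aromatase Inhibitors (AIs) at 12- and 24-months after enrollment". Item 12 (Statistical Considerations) repeats that it is part of the primary objective. It also names the measure: "The primary endocrine therapy outcome will be adherence to endocrine therapy assessed via the electronic medical records". The crude adherence rates are to be compared by simple logistic regression.

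Under Power and Sample Size Considerations in item 12, the control rate is an assumption: "We assume approximately 50% of patients randomized to usual care in our study will be adhering to endocrine therapy" at one year after starting. The effect is given as "50% vs. 75%, adherence in control and intervention groups, respectively". The size follows: "Group sample sizes of 76 patients per group (or $N = 152$) provides 90% power to detect an absolute difference of 25" percentage points, "at a two-sided 0.05 significance level". The next sentence takes 70% of 172 as 120 women prescribed endocrine therapy and ends: "thus an $N = 120$ will also allow for sufficient statistical power". No percentage is attached to 120.

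**The concern.** The closing sentence presents 120 as following from the calculation just before it, but 120 is 32 women, or 21%, fewer than 152. The only power level that the section uses to size either primary endpoint is 90%, and the number of women expected for this endpoint does not reach it.

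What is at stake is how a null result would be read. If the intervention really raised adherence from 50% to 75%, a trial with 90% power would miss it about one time in ten. With the expected number it would be missed nearly two times in ten. A reader of the plan cannot see this, because no figure is given for the sample that the trial expects to analyse.

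**Working it through.** **Inputs, all from the plan**
- Control rate p1 = 0.50 and intervention rate p2 = 0.75 (item 12, power section).
- Two-sided alpha 0.05, so z = 1.960; power 90%, so z = 1.2816 (same place).
- Stated size 76 per group (same place).
- Women expected: 0.70 × 172 = 120.4, taken as 120 (same place).
- Randomization 1:1, stratified by hormone receptor status (item 3(d)), so about 60 per arm. The even split is an expectation.

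**Formulas** (two proportions, pooled variance under the null, no continuity correction)
- A = √[2·p̄(1 − p̄)] with p̄ = (p1 + p2)/2, and B = √[p1(1 − p1) + p2(1 − p2)].
- n per group = (z_α·A + z_β·B)² / (p2 − p1)².
- Power = Φ{[(p2 − p1)·√n − z_α·A] / B}.

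Here p̄ = 0.625, A = √0.46875 = 0.6847 and B = √0.4375 = 0.6614.

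**Step 1: reproduce the plan's figure**
- n = (1.960 × 0.6847 + 1.2816 × 0.6614)² / 0.0625 = (1.3419 + 0.8477)² / 0.0625 = 76.7, so 77 per group against 76 stated.
- Power at n = 76: (0.25 × 8.718 − 1.3419)/0.6614 = 1.266, and Φ = 0.897.
- Exact enumeration of the chi-square test at 76 per arm gives 0.902.
- The continuity-corrected formula would need 85 per group and the one-sided one 63, so neither is what the plan used.

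The statement of 90% for 152 women is therefore sound.

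**Step 2: the same calculation at 60 per arm**
- (0.25 × 7.746 − 1.3419)/0.6614 = 0.899, and Φ = 0.816.

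| Method, 60 per arm | Power |
|---|---|
| Pooled z | 81.6% |
| Unpooled z | 83.3% |
| Exact, chi-square test | 81.8% |
| Exact, Wald test from logistic regression | 81.4% |
| Exact, likelihood-ratio test | 81.8% |

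The Wald and likelihood-ratio rows correspond to the planned logistic regression. Fisher's exact test would give 76.0%, but it is not the planned test.

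**Step 3: difference detectable at 90% with 60 per arm**
- 27 points (50% versus 77%): 87.7%.
- 28 points (50% versus 78%): A = √0.4608 = 0.6788, B = √0.4216 = 0.6493, (0.28 × 7.746 − 1.960 × 0.6788)/0.6493 = 1.291, and Φ = 0.902.

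The answer is about 28 points.

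**Step 4: enrolment that would deliver 152**
- 152/0.70 = 217.1, so about 218 women randomised, against 172 planned.

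**Step 5: margin** (illustrative assumptions, not the plan's)
- 10% without usable data, 54 per arm: (0.25 × 7.348 − 1.3419)/0.6614 = 0.749, and Φ = 0.773.
- Alpha 0.025, a Bonferroni split over two primary endpoints, 60 per arm: (1.9365 − 2.2414 × 0.6847)/0.6614 = 0.608, and Φ = 0.728.

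**The case against.** The strongest reply is that nothing in the section is arithmetically false. The 152 reproduces, 70% of 172 is 120, and 90% is claimed only for 152. For 120 the plan says only that power is sufficient, and 82% is above 80%. The same section presents 81% as its power for chemotherapy dose adjustment if 10% of the intervention arm drops out, so a figure in the low eighties is within what the plan accepts. (That 81% is cited only for the level it represents; nothing here depends on whether it reproduces.) The plan also expects little loss and will use prescription refill data for women lost to follow-up, so the 10% case is not its own expectation.

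All of this stands, and it limits the point. What remains is that the plan sizes a primary endpoint at one number, expects a smaller one, and gives no power for the smaller one.

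Three stronger readings are tempting, and the documents do not support them:
- A reader might infer from the word linking 120 to the preceding calculation that 90% is claimed for 120 as well. The text does not say so.
- A reader might infer that the sentence survives from the earlier target of 250, where 70% is 175 and exceeds 152. Other text does keep larger numbers: the randomization section still gives 125 per arm, and the insulin calculation arrives at 224. But the sentence itself uses 172, and its history is not documented.
- A reader might infer that moving the primary measure to medical records raises the control rate well above 50% and so changes the power. The plan does not say that the record captures continuation only. The cohort figures in its Background also fit the planned rate: 31% discontinued and 28% of continuers were non-adherent, so 0.69 × 0.72 = 0.497.

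**Conclusion.** The point holds as a gap in the stated power. With the roughly 120 women expected, power for 50% versus 75% is about 82% (81% to 83% across the methods that fit the plan's calculation or its planned test). That is about 8 points below the level used for sizing. The effect detectable at 90% power is about 28 points instead of 25.

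This rests on the plan's own rates and alpha, its 70% share and an even split between arms, and it assumes that every one of those women has usable data. The margin above 80% is thin: either illustrative allowance, for loss (about 77%) or for multiplicity (about 73%), takes power below it. The plan says only that a Bonferroni correction will be considered, so the second allowance is a possibility and not a commitment. The finding does not invalidate the endpoint or the trial.

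**What to change.** Replace the closing sentence of the endocrine-therapy calculation in item 12 with: *With about 120 women (60 per arm), power is about 82% for 50% versus 75% adherence at two-sided 0.05; at 90% power the detectable difference is about 28 points (50% versus 78%). These figures make no allowance for loss or for multiplicity.*

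If the investigators expect women without usable adherence data, or decide to apply a Bonferroni correction, they should add the corresponding figure. As illustrations, power is about 77% with 10% lacking data and about 73% at alpha 0.025.

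The cost is a wording change and a less favourable stated figure. Enrolment, analysis and conduct do not change.
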